1 OVERVIEW AND INVESTIGATIONAL PLAN

1.1 STUDY DESIGN AND RANDOMIZATION

This is a Phase 3, multicenter and multinational, randomized, double-blind, placebo-controlled, parallel-group study to evaluate the efficacy and safety of sotagliflozin added to metformin in patients with type 2 diabetes mellitus (T2DM) who have inadequate glycemic control on metformin.

All patients will have a Screening Period consisting of a Screening phase of up to 2 weeks and a 2-week single-blind Run-in phase prior to randomization. In order to qualify for randomization, patients must demonstrate compliance based upon pill count ($\geq 80\%$) during the Run-in phase.

Randomization will be performed via interactive response technology (IRT), where forced randomization is not allowed, and stratified by:

- Hemoglobin A1c (HbA1c) at Screening ($\leq 8.0\%$, $> 8.0\%$)
- Mean systolic blood pressure (SBP) at Screening (< 130 mmHg, ≥ 130 mmHg)

Following randomization, patients will have a 26-week, double-blind Core Treatment Period, a 53-week double-blind extension, and a 4-week post-treatment Follow-up period to collect safety information (patients who prematurely discontinue the study treatment are expected to continue in the study).

A total of 500 patients ≥ 18 years of age will be randomly assigned 1:1 to 1 of the following 2 treatment groups:

- sotagliflozin 400 mg
- Placebo

Ambulatory Blood Pressure Monitoring substudy (ABPM substudy)

Approximately 200 of the 500 enrolled patients who have a mean SBP ≥ 130 mmHg at screening are expected to participate in an ABPM substudy where patients will have blood pressure measured by a validated ABPM device.

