1.3 DETERMINATION OF SAMPLE SIZE

The sample size/power calculations are based on the primary variable, Change from Baseline to Week 26 in HbA1c. Assuming a common standard deviation (SD) of 1.2% and using a 2-sided test at a 0.05 α -level, 250 patients per arm will have 99% power to detect a treatment difference of 0.6% in mean HbA1c Change from Baseline to Week 26 between sotagliflozin 400 mg and placebo.

The sample size/power calculations for ABPM substudy are based on the primary variable, Change from Baseline to Week 12 in average 24-hour SBP in patients with SBP ≥ 130 mmHg at Screening. Assuming a common SD of 15 mmHg and using a 2-sided test at a 0.05 α -level, 100 patients per arm will provide 90% power to detect a treatment difference of 7 mmHg in average 24-hour SBP Change from Baseline to Week 12 between sotagliflozin 400 mg and placebo.

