2.1.4.2 AEs variables

AE observation period

- Pre-treatment AEs are AEs that developed or worsened or became serious from the signed informed consent date up to first dose of double-blind IMP
- Treatment-emergent AEs are AEs that developed or worsened or became serious during the treatment-emergent AE period.
- Posttreatment AE are AEs that developed or worsened or became serious during the posttreatment period.

All adverse events (including SAEs, AESI and EOSI) will be coded to a lower-level term (LLT), preferred term (PT), high-level term (HLT), high-level group term (HLGT), and associated primary system organ class (SOC) using the version of MedDRA currently in effect at Sanofi at the time of database lock.

The occurrence of AEs (including SAEs, AESI and EOSI) will be recorded from the time of signed informed consent until the end of the study (see [Section 2.1.4](#)) or the resolution/stabilization of all SAE, AESI and EOSI.

AESI

- Pregnancy
- Symptomatic overdose with IMP/NIMP
- Alanine aminotransferase (ALT) increase >3 times upper limit of normal (ULN)

EOSI

- Major adverse cardiovascular events (MACE) [cardiovascular death, myocardial infarction, or stroke] and other specific cardiovascular (CV) events (eg, heart failure requiring hospitalization)
- Severe hypoglycemia
Genital mycotic infections (to include vulvovaginal candidiasis in females and candida balanitis in males)
- Urinary tract infections
- Clinically relevant volume depletion and events related/possibly related to volume depletion
- Diarrhea
- Pancreatitis
- Bone fractures
- Venous thrombotic events, to include deep venous thrombosis and thromboembolism (to include pulmonary embolism)
- Diabetic ketoacidosis

Statistical Analysis Plan**Version: 3**

Lexicon Pharmaceuticals Protocol No. EFC14834

Date of Issue: 10 December 2019

Covance Study ID: 000000150525

- Renal events, to include 50% decline in eGFR, end stage kidney disease, renal death
- Malignancies of special interest (breast, bladder, renal cell, Leydig cell, pancreatic, prostate, and thyroid cancer)
- AE leading to an amputation.

A Clinical Endpoint Committee(s) (CEC) will, in a blinded manner review and adjudicate all deaths, myocardial infarction, stroke, unstable angina requiring hospitalization, and heart failure requiring hospitalization, selected renal events, bone fracture, and diabetic ketoacidosis.

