2.4.5.2 Analyses of AEs

Generalities

The primary focus of AE reporting will be on treatment-emergent AEs. Pretreatment and posttreatment AEs will be described separately.

If an AE date/time of onset (occurrence, worsening, or becoming serious) is incomplete, an imputation algorithm will be used to classify the AE as pretreatment, treatment-emergent, or posttreatment. The algorithm for imputing date/time of onset will be conservative and will classify an AE as treatment emergent unless there is definitive information to determine it is pretreatment or posttreatment. Details on classification of AEs with missing or partial onset dates are provided in [Section 2.5.3](#).

Adverse event incidence tables will be presented by SOC, HLGT, HLT, and PT, sorted by the internationally agreed order for SOCs and alphabetic order for HLGT, HLT and PT within a SOC, the number (n) and percentage (%) of patients experiencing an adverse event. Multiple occurrences of the same event by PT in the same patient will be counted only once in the tables within a treatment phase. The denominator for computation of percentages is the safety population within each treatment group.

Sorting within tables ensures the same presentation for the set of all adverse events within the observation period (pretreatment, treatment-emergent, and posttreatment). For that purpose, the table of all treatment-emergent adverse events presented by primary SOC and PT sorted by the internationally agreed SOC order and decreasing frequency of PTs within SOCs in the sotagliflozin group will define the presentation order for all other similar tables unless otherwise specified. In case of equal frequency regarding PTs, alphabetical order will be used.

Analysis of all treatment-emergent AEs

The following treatment-emergent AE summaries will be generated during the 26-week core and the 79-week entire treatment periods respectively in the safety population.

- Overview of treatment-emergent AEs, summarizing number (%) of patients with any
 - Treatment-emergent AE
 - Serious treatment-emergent AE
 - Treatment-emergent AE leading to death
 - Treatment-emergent AE leading to permanent treatment discontinuation.
- All treatment-emergent AEs by primary SOC, showing number (%) of patients with at least 1 treatment-emergent AE, sorted by internationally agreed order of primary SOC.

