- All treatment-emergent AEs by primary SOC, HLGT, HLT, and PT, showing number (%) of patients with at least 1 treatment-emergent AE sorted by the SOC internationally agreed order. The other levels (HLGT, HLT, PT) will be presented in alphabetical order.
- Number (%) of patients experiencing Treatment-emergent AEs presented by PT, sorted by decreasing incidence of PT in the sotagliflozin group.
- All treatment-emergent AEs by primary SOC and PT, showing the number (%) of patients with at least 1 treatment-emergent AE, sorted by the internationally agreed SOC order and by decreasing incidence of PTs within each SOC in the sotagliflozin group. This sorting order will be applied to all other similar tables, unless otherwise specified.

- All treatment-emergent AEs regardless of relationship and related to IMP by primary SOC, HLGT, HLT and PT, showing the number (%) of patients with at least 1 treatment-emergent AE, sorted by the internationally agreed SOC order. The other levels (HLGT, HLT, PT) will be presented in alphabetical order.
- All treatment-emergent AEs by maximal severity, presented by primary SOC and PT, showing the number (%) of patients with at least 1 treatment-emergent AE by severity (ie, mild, moderate, or severe), sorted by the sorting order defined above.
- Common treatment-emergent AEs (PTs with an incidence $\geq 2\%$ in any treatment group) by primary SOC, HLGT, HLT, and PT, sorted by internationally agreed order of SOCs. The other levels (HLGT, HLT, PT) will be presented in alphabetic order.
- Summaries of common treatment-emergent AEs (PTs with an incidence $\geq 2\%$ in any treatment group) will be provided as appropriate by primary SOC and PT and by demographic factors including gender (Male, Female), age group (<50 , ≥ 50 to <65 , ≥ 65 years of age), race (White, Black or African American, Asian, Other), baseline SBP category (<130 mmHg, ≥ 130 mmHg), and baseline eGFR category (≥ 30 to <60 mL/min/1.73 m² [Moderate decrease in GFR], ≥ 60 to <90 mL/min/1.73 m² [Mild decrease in GFR], and ≥ 90 mL/min/1.73 m² [Normal]). SOC will be sorted by internationally agreed order and the PT by decreasing incidence within each SOC in the sotagliflozin 400 mg group, as described above.
- TEAEs (PTs with an incidence $\geq 5\%$ in any treatment group) by primary SOC, HLGT, HLT, and PT, sorted by internationally agreed order of SOCs. The other levels (HLGT, HLT, PT) will be presented in alphabetic order.

Analysis of all treatment emergent SAE(s)

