- ii. recorded in eCRF “Renal Event – Dialysis”,
- iii. identified as “Renal transplant” in eCRF “Other procedure”,

Renal death will be part of all deaths specified above.

Other EOSIs

For EOSIs that are not adjudicated, the number (%) of patients with at least one event will be summarized by treatment group and by PT (as identified in [Table 3](#) in [Section 2.1.4.2](#)).

Severe hypoglycemia will be included in the summary of hypoglycemia (See [Section 2.4.5.1](#)).

AE leading to an amputation is described in the section below.

Analysis of Amputation

The number (%) of patients with amputation will be summarized by treatment group and by PT and LLT during the study (ie, regardless of on- or post-treatment). Amputation is a procedure recorded in eCRF form “Other Procedures related to Amputation”. Patients who had a procedure related to amputation will be listed.

The number (%) of patients with an “AE leading to an amputation” will be summarized by treatment group and by PT. The “AE leading to an amputation” is determined by the AE identifier recorded in eCRF “Other Procedures related to Amputation” when “AE correction” is chosen as the reason for the amputation procedure.

In addition, the number (%) of patients with an “AE potentially leading to an amputation” will be summarized by treatment group and by PT (as identified in [Table 3 in Section 2.1.4.2](#)). These PTs in [Table 3](#) were requested by the European Medicines Agency (EMA)/ Pharmacovigilance Risk Assessment Committee (PRAC) Assessment Report, 9 February 2017). The associated list will be provided as well, with patients who had an amputation procedure flagged. “AE potentially leading to an amputation” represents the condition that may potentially lead to the amputation procedure, but not in all cases an amputation has occurred.

Analysis of pretreatment and posttreatment AEs

- All pretreatment AEs by primary SOC and PT, showing the number (%) of patients with at least 1 pretreatment AE, sorted by the internationally agreed SOC order and decreasing incidence of PTs within each SOC in the sotagliflozin group
- All posttreatment AEs by primary SOC and PT, showing the number (%) of patients with at least 1 posttreatment AE, sorted by the internationally agreed SOC order and decreasing incidence of PTs within each SOC in the sotagliflozin group.

Listings

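### Adverse-event percentages for terms that only one sex can have are divided by the whole arm, and no planned table guarantees the incidence of genital mycotic infection among women or among men

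*SAP*

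**What the plan says.** SAP 2.4.5.2 (Generalities) states one rule for adverse-event incidence tables: "The denominator for computation of percentages is the safety population within each treatment group". Protocol 11.4.3.1 has the same sentence. Neither document gives a sex-specific denominator anywhere.

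SAP 2.4.5.2 then plans several kinds of table:

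- Tables of all TEAEs with no frequency cut-off, by PT and by system organ class.
- A table of common events, defined as "Common treatment-emergent AEs (PTs with an incidence $\geq 2\%$ in any treatment group"), and a further table with a 5% cut-off set in the same way.
- Summaries of those same 2% common events, which "will be provided as appropriate by primary SOC and PT and by demographic factors including gender (Male, Female"). Appendix G confirms that the subgroup analysis of adverse events covers common TEAEs only.
- For EOSIs that are not adjudicated, "the number (%) of patients with at least one event will be summarized by treatment group and by PT". There is no cut-off and no split by sex.

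SAP 2.1.4.2 describes one of those EOSIs as "Genital mycotic infections (to include vulvovaginal candidiasis in females and candida balanitis in males"). Appendix F lists eight PTs for it. Five can occur in one sex only: balanitis candida, fungal balanitis, vulvovaginal candidiasis, vulvovaginal mycotic infection and candida cervicitis. Three can occur in either sex: genital candidiasis, genital infection fungal and urogenital infection fungal. Table 3 of the SAP adds prostate cancer among the malignancies of special interest, and the venous thrombotic list in Appendix F includes penile vein thrombosis.

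**The concern.** For a single-sex PT, the whole-arm denominator counts patients who cannot have the event. The resulting percentage is not the risk that a woman or a man on treatment faces, which is what a clinician reads from such a row. The same diluted percentage decides whether the PT enters the 2% and 5% tables. The by-gender summary takes only PTs that have already passed the whole-arm 2% test, so it cannot rescue a PT that failed because of dilution.

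This matters most for genital mycotic infection. Protocol 4.6 names it among the risks to be monitored closely, and protocol Appendix D gives separate hygiene advice to females and to uncircumcised males. Hypoglycemia has a planned summary by gender (SAP 2.4.5.1), but the genital mycotic EOSI has none.

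**Working it through.** **Inputs.** The planned arm size is 250 (SAP 1.3: "250 patients per arm will have 99% power to detect a treatment difference of 0.6"%; allocation 1:1 in SAP 1.1). The cut-offs are 2% and 5% of an arm (SAP 2.4.5.2). The documents give no adverse-event rate and no sex split, so there is no stated figure to reproduce. Sex is not a randomization stratum. I assume that the at-risk sex is 50% of the arm and show 40% and 60% as a range. Actual safety-population sizes may differ from 250.

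**Dilution.** Reported % = cases / 250 = (cases / n of that sex) × (n of that sex / 250). The reported figure is therefore the within-sex incidence times that sex's share. At 50/50, 4 affected women are 4/125 = 3.2% of women and 4/250 = 1.6% of the arm.

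**Cut-offs.** 0.02 × 250 = 5 patients. 0.05 × 250 = 12.5, so 13 patients.

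| Share of at-risk sex | n of that sex | Within-sex % at 5 cases (enters 2% table) | Within-sex % at 4 cases (left out) | Within-sex % at 13 cases (enters 5% table) |
|---|---|---|---|---|
| 40% | 100 | 5.0% | 4.0% | 13.0% |
| 50% | 125 | 4.0% | 3.2% | 10.4% |
| 60% | 150 | 3.3% | 2.7% | 8.7% |

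**Chance that one arm reaches the 2% cut-off.** These are binomial tail probabilities at an assumed true within-sex rate of 3%. The whole-arm rule needs at least 5 cases. The same-sex rule needs at least 2 of 100, 3 of 125 or 3 of 150.

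| Share of at-risk sex | Whole-arm rule | Same-sex rule |
|---|---|---|
| 40% | 18.2% | 80.5% |
| 50% | 32.2% | 72.7% |
| 60% | 46.9% | 83.1% |

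At a true 4% rate and a 50/50 split the two chances are 56.3% and 88.0%. They refer to a single arm; a PT enters the table if either arm qualifies.

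**Can the by-sex rate be recovered?** For one single-sex PT it can: take the count and divide by the number of that sex in the arm. For the grouped genital mycotic EOSI it cannot be done from the by-PT table. Three of the eight PTs do not reveal the patient's sex, and one patient may appear under more than one PT. The number of women, or of men, with any such infection would have to be rebuilt from the patient listings, which do carry sex.

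**The case against.** The strongest reply is that nothing is lost. The all-TEAE tables and the non-adjudicated EOSI tables have no cut-off, so every genital mycotic, prostate or penile term appears there whatever its count. Counts are shown by PT and arm, gender is summarised by arm, and cases over the whole arm is a legitimate quantity, namely the risk in the enrolled population. Protocol and SAP agree on it. For the pooled genital mycotic row, the whole arm is the correct denominator. All of this stands. What it leaves is that the percentages printed for single-sex PTs are diluted, that the cut-offs act on those diluted percentages, and that the pooled EOSI has no by-sex counterpart.

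Three stronger readings are tempting, and the documents do not support them:

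- A reader might infer that every reported percentage for these terms is affected. But the by-gender summary, read in the ordinary way, gives within-sex percentages for PTs that reach 2% of an arm, although its denominator is not spelled out.
- A reader might cite the Leydig-cell group as a single-sex category. Table 3 pools a testicular with an ovarian PT, so each PT is single-sex but the group is not.
- A reader might infer that the comparison between arms is distorted. If the sex split is the same in both arms, the share cancels from the relative risk. A shift needs a chance imbalance, and SAP 2.4.5 treats safety descriptively with no testing.

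**Conclusion.** The point holds as a reporting improvement. Percentages for single-sex PTs equal the within-sex incidence times that sex's share of the arm. With 250 per arm, a PT affecting up to 3.2% of the at-risk sex (4 of 125 at 50/50) stays out of the 2% and by-gender tables; entry needs 4.0%, or 5.0% to 3.3% over shares of 40% to 60%. The factor of about one half rests wholly on the assumed equal split.

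A reader might also conclude that events are hidden or that an efficacy result is at risk. Neither follows: the tables without a cut-off show all events, and no efficacy analysis uses these percentages. The EOSI text gives no denominator of its own, so I read it as falling under the general rule of the same section. The lasting gap is that no planned table guarantees the incidence of genital mycotic infection among women or among men.

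**What to change.** In SAP 2.4.5.2:

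1. Add a list of single-sex PTs, defined at PT level so that the testicular and ovarian Leydig-cell PTs are handled separately. For these, the denominator is the number of safety patients of that sex in the arm, and the 2% and 5% cut-offs apply to that percentage.
2. Show the genital mycotic infection EOSI for females and for males, each over the safety patients of that sex in the arm, next to the pooled whole-arm row.

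The data are already collected. The cost is the PT list, minor table programming, and some rows with a different N that need a footnote. The parallel sentence in protocol 11.4.3.1 differs from the revised rule, so the SAP should record the departure.
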